**EXPERIMENTAL DESIGN SCHEMA**

\* Interim assessment after 14 patients accrue. If 1 or more demonstrates a partial response, or if 4 or more achieve a progression free survival of 4 months, then all 25 participants will accrue to the trial.

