**Study Design:**

Patients who have had previous clinical benefit with first-line anti-EGFR therapy (at least 6 months PFS/PR/CR by RECIST criteria), have subsequently received and progressed on a non-anti-EGFR containing regimen, and have not been exposed to anti-EGFR therapy for at least 4 months will receive panitumumab combined with FOLFIRI (5-fluorouracil, leucovorin, irinotecan) every two weeks with response assessment at 8 week intervals until progression or removal from study treatment due to toxicity.

A modified Gehan 2-stage Phase II design will be employed. In the first stage, 14 participants will be accrued and assessed for response rate and progression free survival. If no objective responses are observed in 14 participants, and fewer than 4 participants are progression-free at the 4 month evaluation, the study will close for futility. If there is at least one response, or at least 4 participants progression-free at 4 months, an additional 11 participants will be accrued.

In addition to response assessment using RECIST 1.1, survival, toxicity information, carcinoembryonic antigen, and blood samples for cell-free DNA and microRNA exploratory analysis will be collected.

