**Statistical Considerations:**

The primary hypothesis is that the combination of FOLFIRI + panitumumab has activity in patients with *RAS/RAF* WT mCRC when introduced as a re-challenge to patients that had previous clinical benefit with first-line anti-EGFR therapy (at least 6 months PFS/PR/CR by RECIST criteria), have received a subsequent non-anti-EGFR containing regimen, and have not been exposed to anti-EGFR therapy for at least 4 months.

As we will not know a priori the response rate to first-line anti-EGFR therapy, nor the median PFS with previous anti-EGFR therapy, and this study will not be restricted to two prior chemotherapy regimens due to treatment patterns in the US, we can't use the cetuximab estimates for this trial. As a result, a modified Gehan 2-stage Phase II design will be employed.

In the first stage, 14 patients will be accrued. Failure to observe a response if the true response is 20% or above would occur with a probability less than 5% (4.4%). Failure to observe at least 4 patients progression-free at the second evaluation (~4 months), would occur with less than 3% probability if the true 4-month PFS rate is 50%, and would occur with more than 95% probability if the true 4-month PFS rate was 10%, which is higher than placebo treatment 4-month PFS seen on the CORRECT trial.[1] As a result, if no objective responses are observed in 14 patients, and fewer than 4 patients are progression-free at the 4 month evaluation, the study will close for futility. If there is at least one response, or at least 4 patients progression-free at 4 months, an additional 11 patients will be accrued. The interim stopping for futility is such that there is a 46% chance of early stopping if the response rate is 5% and the 4-month PFS rate is 10%. This compares to 48.7% early stopping probability for the standard Gehan design if the true response rate is 5%, but allows us to pass the interim stopping condition if PFS suggests enough activity due to re-challenge to expand to a total of 25 patients.

With a total of 25 patients, the standard error of estimate for the response rate estimate and the 4-month PFS rate estimate will not exceed 10%.

All of the patients who met the eligibility criteria (with the exception of those who received no study medication) will be included in the main analyses of response and PFS, and all the secondary or correlative analysis described below.

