### Exploratory Objectives:

1. Collect serial plasma samples to investigate the incidence of *RAS* and *BRAF* mutation in circulating free DNA at baseline, every 2 months, and at the time to progression (and following progression when feasible).
2. Collect serial plasma samples for future biomarker exploration, including the potential investigation of micro-RNA

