## 2.2 Overview of Proposed Study

Eligible patients must have had a prior objective response or a prolonged stable disease (6 months or more) to one prior anti-EGFR based therapy (either cetuximab or panitumumab) in combination with irinotecan (either irinotecan alone or irinotecan plus a fluoropyrimidine). Evidence of progressive disease must have been documented within 6 weeks from their last dose of anti-EGFR therapy. Patients should have been subsequently treated with one or more non-anti-EGFR containing regimens and should be at least 4-month-anti-EGFR-naïve before they can get enrolled on this proposed study. The schema for enrollment is summarized in the figure below.

Patients will be treated on the study with bi-weekly panitumumab in combination with FOLFIRI and the doses recommended by the NCCN guidelines for first or second line treatment. Since patients enrolled on this study are heavily pre-treated, the study will allow some flexibility in the irinotecan and 5-fluorouracil (5-FU) dosing as is detailed in section 5.2. Patients will continue on treatment until evidence of progressive disease or unacceptable toxicity. Response to treatment will be assessed with clinical imaging, which will be performed every 4 cycles (every 8 weeks).

This study will be conducted in compliance with the protocol, Good Clinical Practice (GCP) and the applicable legal and regulatory requirements.

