## 6.2 Dose Modifications/Delays

### 6.2.1 General Information

1. The study will use the NCI Common Terminology Criteria for Adverse Events (CTCAE) version 4.0 to grade toxicities, except for skin- and nail-related toxicities, which must be graded using CTCAE version 4.0 with modifications found in Appendix B. A copy of the version 4.0 can be downloaded from:

<http://evs.nci.nih.gov/ftp1/CTCAE/About.html>

2. Study agents are always held together, regardless of the attribution of the toxicity.
3. There is no maximum dose reduction for irinotecan or 5-FU.
4. Panitumumab has a maximum of two dose level reductions, and will not exceed the 60% dose level according the following table:

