As a result, we will employ a modification of the Gehan 2-stage Phase II design. In the first stage, 14 participants will be accrued. Failure to observe a response if the true response is 20% or above would occur with a probability less than 5% (4.4%). Failure to observe at least 4 participants progression-free at the second evaluation (~4 months), would occur with less than 3% probability if the true 4-month PFS rate is 50%, and would occur with more than 95% probability if the true 4-month PFS rate was 10%, which is higher than placebo treatment 4-month PFS seen on the CORRECT trial.[1] As a result, if no objective responses are observed in 14 participants, and fewer than 4 participants are progression-free at the 4 month evaluation, the study will close for futility. If there is at least one response, or at least 4 participants progression-free at 4 months, an additional 11 participants will be accrued. The interim stopping for futility is such that there is a 46% chance of early stopping if the response rate is 5% and the 4-month PFS rate is 10%. This compares to 48.7% early stopping probability for the standard Gehan design if the true response rate is 5%, but allows us to pass the interim stopping condition if PFS suggests enough activity due to re-challenge to expand to a total of 25 participants.

With a total of 25 participants, the standard error of estimate for the response rate estimate and the 4-month PFS rate estimate will not exceed 10%.

All of the participants who met the eligibility criteria (with the exception of those who received no study medication) will be included in the main analyses of response and PFS, and all the secondary or correlative analysis described below.

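### Cycle-tied scans with a ±2-week window let the second scan fall after 4 months and can raise the 4-month Kaplan-Meier PFS; calendar-anchored scans, a narrower window and a stated reading day are a cheap improvement

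*Combined protocol and SAP*

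**What the plan says.** **Scan schedule.** The synopsis (Study Design) describes "response assessment at 8 week intervals until progression". Section 2.2 says: "Response to treatment will be assessed with clinical imaging, which will be performed every 4 cycles (every 8 weeks"). Table 10.0 puts imaging and response assessment on day 1 of cycle 5, and its footnote d repeats this at cycles 9, 13, 17 and so on. The second scan therefore belongs to day 1 of cycle 9, after eight cycles.

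**What can move it.** Section 5.1 defines a cycle as running from one dose to the next. Section 10.0 lets a cycle be lengthened by up to 5 days or shortened by up to 2, and gives scans a ±2-week window. Section 6.2.1 adds: "Study agents are always held together, regardless of the attribution of the toxicity". Item 9 of that section allows treatment to resume up to 28 days after the last dose.

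**How 4-month PFS is used.** The gate is worded as a visit in Section 13.1 ("Failure to observe at least 4 participants progression-free at the second evaluation (~4 months") and in the synopsis ("fewer than 4 patients are progression-free at the 4 month evaluation"). It is worded as a time in the design schema ("if 4 or more achieve a progression free survival of 4 months"). Section 13.1 also says that with 25 participants "the standard error of estimate for the response rate estimate and the 4-month PFS rate estimate will not exceed 10" percent. PFS is part of the primary endpoint, and Section 13.3 estimates it by Kaplan-Meier.

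**Dating of progression.** The PFS definition at the end of Section 11.1 runs to progression or death and does not say which date counts as progression. Section 11.1.5 ends response duration on the date progression is objectively documented. Section 11.1.2 has one explicit rule: an initially unconfirmed FDG-PET finding that later CT confirms is dated back to the abnormal FDG-PET scan.

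**The concern.** A participant who progresses after the first scan, and whose second scan falls after day 122, counts as progression-free at 4 months when progression is dated to the scan. Early scans do not offset this. They miss progressions that occur between the scan and day 122, and so also push the reading up. The shift therefore goes one way and does not shrink with more participants.

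At stake is the 4-month PFS rate, an estimate on a primary endpoint with its own stated precision. A standard error of at most 10% describes random error only. A reader comparing the rate with another series would have no way to see how much of it came from scan timing.

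**Working it through.** **1. The plan's own figures.** For stage 1 (n = 14) and the final sample (n = 25):

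- P(0 responses at 20%) = 0.8^14 = 4.4%.
- P(fewer than 4 progression-free), X ~ Bin(14, p): 2.87% at p = 0.50 and 95.6% at p = 0.10.
- Early stopping at response rate 5% and PFS 10%, treating the two gates as independent: 0.95^14 × 0.9559 = 0.4877 × 0.9559 = 46.6% (printed as 46%).
- Largest SE: √(0.5 × 0.5/25) = 10.0%.

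All reproduce.

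**2. Day counts.** Four months = 4 × 365.25/12 = 121.75 days.

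- Nominal second scan: 8 × 14 = day 112. The window gives days 98 to 126.
- One 28-day cycle and no use of the window: 7 × 14 + 28 = day 126.
- Permitted cycle lengths without any hold: cycle 9 day 1 falls between 8 × 12 = day 96 and 8 × 19 = day 152.

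**3. Kaplan-Meier reading at day 122, window only.** Assumptions, none given in the documents: exponential PFS with S(t) = r^(t/b); scan 1 uniform on 56 ± w days and scan 2 uniform on 112 ± w; progression dated to the scan; deaths and clinically triggered assessments ignored. Here b = 121.75 if r is a day-122 rate, and b = 112 if r is a week-16 rate.

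Reading = late × mean S(scan 1) + (1/2w) × ∫S(t)dt from 112 − w to min(121.75, 112 + w), with late = max(0, (112 + w − 121.75)/2w).

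With w = 14, late = 4.25/28 = 0.152. At day-122 rates:

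- r = 10%: 0.152 × 0.351 + 0.107 = 16.0%.
- r = 50%: 0.152 × 0.728 + 0.454 = 56.5%.

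The SEs at n = 25 are √(0.1 × 0.9/25) = 6.0% and 10.0%, so the shifts are 1.0 and 0.65 SE. At week-16 rates the readings are 13.8% and 53.8%.

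**4. Adding cycle drift.** With cycle lengths uniform on 12 to 19 days (mean 15.5, so cycle 9 day 1 averages 8 × 15.5 = day 124) and the ±2-week window, simulation puts 58% of second scans after day 122. The readings are about 22.7% and 62.4%.

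**5. Which part of the remedy matters.** True rates are day-122 rates.

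| Schedule | True 10% | True 50% |
|---|---|---|
| Cycle-tied, 12–19-day cycles, ±2 weeks | 22.7% | 62.4% |
| Cycle-tied, 12–19-day cycles, ±1 week | about 23% | about 63% |
| Calendar-anchored, ±2 weeks | 16.0% | 56.5% |
| Calendar-anchored, ±1 week | 12.1% | 52.9% |

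Narrowing the window without anchoring gains nothing. Anchoring without narrowing still lets scans reach day 126. With both, the last permitted second scan is day 112 + 7 = 119. At week-16 rates the anchored ±1-week readings are 10.0% and 50.0%.

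**6. The reading day.** If the curve were read at day 112, half the second scans would come later under either window. Week-16 rates of 10% and 50% would then read 21.8% and 61.5% (±2 weeks) or 21.2% and 60.9% (±1 week).

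**7. The gate.** Counted at the visit, week-16 rates with the ±2-week window give p = 0.1014 and 0.5006. P(fewer than 4) is then 95.4% and 2.8%, with joint stopping 46.5%. If 10% and 50% are instead day-122 rates observed at day 112 (p = 0.1202 and 0.5285), the figures are 92.2%, 1.7% and 45.0%. A late scan lowers a visit-based count: a 50% day-122 rate is 48.8% by day 126. False stopping at response rate 20% and PFS 50%, with independent gates, is 0.0440 × 0.0287 = 0.13%.

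**The case against.** **The plan already promises 8-week scans, and the window lets a site pull a delayed scan back to week 16.** True, and sites that do so will see less of the effect. But nothing requires it, and the calendar attaches the scan to the cycle.

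**Nothing defines 4 months as day 122 or says the curve is read there.** Also true. The 10% ceiling is a plain binomial SE. If the rate is the proportion progression-free at the second evaluation, week-16 rates read 10.1% and 50.1%, essentially unbiased. The protocol itself treats 2 months as 4 cycles: Section 1.0 plans "circulating free DNA at baseline, every 2 months, and at the time to progression", and Section 9.0 draws that blood before cycles 1, 5, 9 and 13. Against this, Section 13.3 names Kaplan-Meier for PFS and the schema words the gate as a duration, so both readings are open.

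**The gate sentence is not at fault.** This stands. A reader might infer that late scans make the gate too easy to pass or that the printed interim figures are wrong. The documents support neither: the figures reproduce, they hold on the week-16 convention, and a late visit lowers the count.

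**Dating progression to the scan is an inference.** It is the natural reading of Section 11.1.5, but a reader should not take that as the only dating rule, because the FDG-PET rule in Section 11.1.2 is another.

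**No success criterion uses the 4-month rate at the final analysis.** Correct, which keeps this an improvement and not a flaw in the design.

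**Conclusion.** The point holds as a cheap improvement to the estimate of 4-month PFS. The schedule as written allows second scans after day 122. If progression is dated to the scan and the Kaplan-Meier curve is read at day 122, the rate is pushed upward. The stage sizes, the printed interim figures and the stopping rule are not in error.

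The size is illustrative. It rests on exponential PFS, uniform timing and ignoring deaths and clinically triggered assessments, which would reduce the shift (Table 10.0, footnote x, allows assessment when clinically indicated). The window alone adds 6.0 and 6.5 points at true day-122 rates of 10% and 50%. A reader might take these as a ceiling. They are not one for this schedule, because they contain no cycle drift; with cycles uniform on 12 to 19 days the shifts are about 12.7 and 12.4 points.

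Nor should a reader infer that the fix recovers the whole shift. At day-122 rates it removes 16.0 − 12.1 = 3.9 points (0.65 SE) and 56.5 − 52.9 = 3.6 points (0.36 SE) of the no-drift shift, and more if cycles drift. The remainder arises because a scan near day 112 reports status about ten days before the reading day.

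**What to change.** - **Sections 2.2 and 10.0, Table 10.0 and its footnotes:** schedule tumour imaging at weeks 8, 16, 24 and so on from cycle 1 day 1, whatever the dose delays, with a ±1-week window. Both parts are needed.
- **Schema, synopsis (Study Design and Statistical Considerations) and Section 13.1:** define the gate as progression-free status at the week-16 scan, with progression or death at or before that scan counted as failure. State that 10% and 50% are week-16 rates, so the printed figures stand. State how a participant without a week-16 scan is counted. This matters with a threshold of 4 in 14, because footnote z does not treat a missed progression assessment off treatment as a deviation.
- **Section 13.3:** date progression to the scan or assessment that documents it, keeping the FDG-PET exception in Section 11.1.2. Read the 4-month Kaplan-Meier rate at day 122, after the week-16 window closes on day 119.

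The cost is wording and calendar edits, with about the same number of scans on treatment and no change to dosing rules. Sites lose some scheduling flexibility. After a delay, imaging may separate from the correlative blood draw on cycle day 1. The PFS estimate may come out slightly less favourable.

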### **13.2 Sample Size Accrual Rate**

In the event the study progresses to the second stage, 25 evaluable participants (received at least 1 cycle of treatment) will be enrolled on this study. The enrollment will be complete within 2 years from activation (accrual of 1-2 participants per month).

### **13.3 Statistical Analysis Plan**

Progression-free survival will be estimated using the product-limit method of Kaplan and Meier. As secondary endpoints, we will investigate the impact of PFS and response on prior anti-EGFR therapy and the time since last anti-EGFR exposure on the response rate and PFS on the current study.

#### **Analysis of Correlative Endpoints:**

Because of the limited sample size inherent to phase II studies, the analysis of correlative endpoints is primarily exploratory. Standard descriptive methods will be used to summarize the role of mutational status and other studies. If the combination is not found to have sufficient activity, these patterns may help explain the lack of activity. If sufficient activity is found, then participants who experience an objective response will be compared to those who did not in terms of correlates. Estimates of variation will also prove useful for future clinical research on this regimen. Formal testing of these comparisons is not planned. All analysis will clearly document the exploratory nature of these studies, although no attempt will be made to adjust for multiple comparisons inherent in correlative studies.

## **14.0 HUMAN SUBJECT ISSUES**

---

### **14.1 Institutional Review Board**

In accordance with City of Hope policies, an Institutional Review Board (IRB) that complies with the federal regulations at 45 CFR 46 and 21 CFR 50, 56 and State of California Health and Safety code, Title 17, must review and approve this protocol and the informed consent form prior to initiation of the study. All institutional, NCI, Federal, and State of California regulations must be fulfilled.

### **14.2 Recruitment of Participants**

Participants will be identified from COH medical oncology clinics.

### **14.3 Advertisements**

Advertisements to include print, media (radio, television, billboards), telephone scripts, lay summary to be posted on City of Hope's public Clinical Trials On-LineSM website, etc., will be reviewed and approved by the IRB prior to their use to recruit potential study participants.

### **14.4 Study location and Performance Sites**

This study will be performed at COH.

### **14.5 Confidentiality**

This research will be conducted in compliance with federal and state of California requirements relating to protected health information (PHI). The study will record individual response to study agents and any side effects, and this will be linked to the participant's identity using a coded study number. The principal investigator, co-investigators, and laboratory technicians will have access to this information,

but all information will be treated confidentially. No identifiers will be used in any subsequent publication of these results.

#### **14.6 Financial Obligations and Compensation**

The study agent, panitumumab, will be provided free of charge by Amgen, Inc.; the remaining study agents, which are standard of care drugs - leucovorin, 5-FU, and irinotecan - will be the responsibility of the research participant and/or the participant's insurance carrier. The standard of care procedures provided will be the responsibility of the research participant and/or the insurance carrier. The research participant will be responsible for all copayments, deductibles, and other costs of treatment and diagnostic procedures as set forth by the insurance carrier. The research participant and/or the insurance carrier will be billed for the costs of treatment and diagnostic procedures in the same way as if the research participant were not in a research study. However, neither the research participant nor the insurance carrier will be responsible for the research procedures related to this study.

In the event of physical injury to a research participant, resulting from research procedures, appropriate medical treatment will be available at the City of Hope to the injured research participant, however, financial compensation will not be available.

The research participant will not be paid for taking part in this study.

#### **14.7 Informed Consent Processes**

The Principal Investigator or IRB approved named designate will explain the nature, duration, purpose of the study, potential risks, alternatives and potential benefits, and all other information contained in the informed consent document. In addition, they will review the experimental subject's bill of rights and the HIPAA research authorization form. Research participants will be informed that they may withdraw from the study at any time and for any reason without prejudice, including as applicable, their current or future care or employment at City of Hope or any relationship they have with City of Hope. Research participants will be afforded sufficient time to consider whether or not to participate in the research.

Should sufficient doubt be raised regarding the adequacy of comprehension, further clarifications will be made and the questionnaire repeated until a satisfactory result is obtained. Prospective research participants who cannot adequately comprehend the fundamental aspects of the research study with a reasonable amount of discussion, education and proctoring will be ineligible for enrollment. For those participants who do comprehend the fundamental aspects of the study, consent will be obtained and documented, followed by eligibility testing. The research team will review the results of eligibility testing and determine if the participant is a candidate for study enrollment.

